11.3 Analysis Methods

11.3.1 Safety

Safety evaluation will include monitoring for adverse events, scheduled laboratory assessments, vital sign measurements, ECGs, and physical examinations. The intensity of adverse changes in physical signs or symptoms will be graded according to the CTCAE version 4. For all other adverse events not listed in the CTCAE, the intensity of events will be assessed by the PI using a 5-point scale as described in [Section 8.3.2](#).

The number of adverse events and the incidence of adverse events will be summarized. Adverse events will be summarized by maximum intensity (as described in [Section 8.3.2](#)) and relationship to study drug for each treatment group. Separate summaries will be provided for all adverse events, serious adverse events, treatment-related adverse events, and other significant adverse events (*e.g.*, adverse events leading to study discontinuation).

Clinical laboratory results will be listed by subject or, as appropriate, summarized descriptively by treatment group, which will include a display of change from baseline. Laboratory values outside of the normal ranges will be identified. Clinically significant hematologic laboratory abnormalities (*i.e.*, meet Grade 3, 4, or 5 criteria according to CTCAE) will be listed and summarized.

Physical examination, vital sign, and ECG data will be listed for each subject at each visit. If appropriate, descriptive statistics for vital signs, both observed values and changes from baseline, will be summarized by treatment group.

11.3.2 Efficacy

All efficacy endpoints will be summarized descriptively using frequency distributions. In addition, 95% confidence intervals will be provided for the proportion of each response/improvement.

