Rationale:	There is a paucity of treatment options for subjects with resistant AML. Recently AML has been shown to be a multi-genetic disease with sub-clonal architecture that evolves spontaneously and in response to treatment. Chemotherapy-resistant leukemic clones can quickly gain dominance by “survival of the fittest” dynamics. One way of targeting minor yet resistant clones is to augment the effectiveness of current chemotherapy drugs. Hromas et al. discovered the importance of the Metnase complex in repairing chemotherapy related DNA damage in leukemia and other cancers (1-3). Screening studies identified ciprofloxacin as a Metnase inhibitor that chemosensitizes leukemic myeloblasts to etoposide chemotherapy (4). The non-overlapping toxicity profiles of ciprofloxacin and etoposide, and their additive effectiveness in this model, make these agents attractive candidates for use in combination in subjects with resistant AML.
Primary Objective:	
In subjects with resistant AML, to
 
 Phase 1b: Establish the maximum tolerated dose (MTD) of oral ciprofloxacin when given in combination with a fixed dose of oral etoposide to subjects with resistant AML. Phase II: Determine the complete response (CR, CRi, and CRp, see Appendix A) rate to treatment with ciprofloxacin and etoposide at the MTD in adults with resistant AML.
Secondary Objectives:	
In subjects with resistant AML, to
 
 Determine the safety and feasibility of treatment with oral ciprofloxacin and etoposide; Measure duration of complete response, of progression free survival and of overall survival following treatment with oral ciprofloxacin and etoposide; and Estimate the incidence of Grade ≥ 3 adverse events following treatment with ciprofloxacin and etoposide.
Study Design:	This is an open-label, single arm, Phase Ib/II study of oral ciprofloxacin and etoposide in subjects with resistant AML. This study is designed to evaluate the complete response rate, the safety profile, and biologic activity of the combination of oral ciprofloxacin and etoposide in subjects with resistant AML. For both study phases, all subjects will receive 1 cycle of induction. At the end of Cycle 1, subjects who demonstrate progressive disease will have completed study treatment. For any subject who demonstrates stable disease or a

partial response, a second cycle of induction will be given. No subject will receive more than 2 cycles of induction.

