2.2 Secondary

In subjects with resistant AML, to

- Determine the safety and feasibility of treatment with ciprofloxacin and etoposide;
- Measure the response duration, progression-free and overall survival (PFS and OS respectively);
- Estimate the incidence of Grade ≥ 3 adverse events following treatment with ciprofloxacin and etoposide at the MTD.

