4.2 Treatment Duration

Phase Ib subjects who developed a DLT with the first cycle will be taken off study at the Cycle 1 Day 28 visit.

For all others, treatment with ciprofloxacin and etoposide will be repeated in 28-day cycles until:

- In Cycle 2, if the treating physician decides that the subject has rapidly progressive disease despite treatment;
- Subject withdrawal of consent for continued participation in the study;
- Inter-current illness that prevents further administration of study treatment;
- Unacceptable toxicity attributed to study treatment with ciprofloxacin and etoposide;
- Completion of 2 cycles of therapy from Day 1, Cycle 1;
- Disease progression defined by >25% increase in marrow blasts ([Appendix A](#));
- If, in the opinion of the PI or treating physician, continuation in the study could be detrimental to the subject's well-being;
- Significant deviation from inclusion/exclusion criteria in the opinion of the PI;
- Lost to follow-up (discontinuation date will be recorded as the date of last contact with subject); and/or
- Termination of the study.

Subjects with an ANC < 500/ μ L at the Day 28 assessment will be treated unless the Day 28 bone marrow shows < 5% cellularity. In that event, treatment will be held and a CBC will be repeated weekly until Day 42. A bone marrow will be repeated no later than Day 42 for subjects who

have treatment held. In the event that the subject does not show bone marrow recovery with a cellularity > 5% by Day 42 of treatment, the subject will be withdrawn from the study.

Table 3. Dosing Modifications

Event	Action
Disease Progression	Stop Therapy
ANC > 500/ μ L, No progression	Resume Therapy
ANC < 500/ μ L, Cellularity > 5%, No progression	Resume Therapy

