6.4 Follow up/Survival

Subjects will have a follow-up visit for the evaluation of adverse events and concomitant medications 28 days (± 7 days) after the last study medication dose.

Follow-up evaluations will be performed for clinically significant abnormal physical examinations or abnormal laboratory findings, 12-lead ECGs, or vital signs, as deemed necessary by the treating physician.. All subjects who have adverse events, whether considered associated

with the use of the study drugs or not, must be monitored to determine the outcome. The clinical course of the adverse event will be followed according to accepted standards of medical practice, even after the end of the period of observation, until a satisfactory explanation is found or the Principal Investigator deems it medically justifiable to terminate follow-up.

All subjects will be followed monthly until: disease progression, death, or until 3 years from the on-study date.

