7.1.2 Efficacy Data

The efficacy outcomes of interest will be CR (including CRi and CRp) as defined in [Appendix A](#). The efficacy variables, which will be used to assess response, include hemoglobin, ANC, platelets, circulating blasts, bone marrow aspirate and biopsy.

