11.1 Determinations of Sample Size

An estimate of 8-24 patients are to be enrolled to Phase Ib portion of the study accounting for a 25% drop-out rate. Precise sample size cannot be defined, as it is dependent on the observed toxicity rate in this phase.

Subjects will be enrolled in the Phase II portion of the study once the MTD has been determined. The primary intention is to determine the complete response rate (CR + CR_i, see [Appendix A](#)) of ciprofloxacin and etoposide given at the MTD to subjects with resistant AML, which is achieved at the end of any treating cycle. The CR rate for AML subjects receiving etoposide alone is approximately 20% (the null hypothesis). We expect that the combination of ciprofloxacin and etoposide will improve the CR rate to 40%. In order to detect this difference with a type I error rate of 0.10 and power of 80%, when the true response rate is 40%, a minimum of 24 subjects who are evaluable for response will need to be accrued, based on the Simon's two-stage Minimax design. Specifically, in the first stage, we will enroll 14 evaluable subjects to this phase. The accrual will be temporarily suspended once the 14th evaluable subject is enrolled, pending response evaluation. If 2 or fewer respond, in these 14 subjects, the study will be stopped. Otherwise, continue to accrue additional 10 evaluable subjects (for a total of 24 evaluable subjects). The null hypothesis of 20% CR will be rejected if 8 or more CRs are observed in 24 subjects. Assuming 20% drop out rate, the total number of subjects to be enrolled to the Phase II portion is 30

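### Response duration, PFS and OS are secondary objectives, but the plan gives no time-to-event method; its only efficacy method, frequency distributions, does not handle censoring

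*Combined protocol and SAP*

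**What the plan says.** Section 11.3.2 (Efficacy) is two sentences long. The first reads "All efficacy endpoints will be summarized descriptively using frequency distributions". The second adds that "95% confidence intervals will be provided for the proportion of each response/improvement".

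Section 2.2 lists among the secondary objectives "Measure the response duration, progression-free and overall survival (PFS and OS respectively"). The synopsis has the same aim: "Measure duration of complete response, of progression free survival and of overall survival following treatment with oral ciprofloxacin and etoposide".

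Section 7.1.2 describes efficacy more narrowly: "The efficacy outcomes of interest will be CR (including CRi and CRp) as defined in" Appendix A. It does not mention the three time endpoints.

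Incomplete follow-up is foreseen. Section 4.2 lists among the reasons for ending treatment "Lost to follow-up (discontinuation date will be recorded as the date of last contact with subject"), and also withdrawal of consent. Section 11.1 states "Assuming 20% drop out rate, the total number of subjects to be enrolled to the Phase II portion is 30".

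Section 6.4 sets the follow-up rule: "All subjects will be followed monthly until: disease progression, death, or until 3 years from the on-study date". The synopsis (Study Duration and Dates) and footnote 13 of Table 1 give the same end points.

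**The concern.** Response duration, PFS and OS are times to event. A subject who is lost, withdraws or is still event-free at analysis contributes a censored time. A frequency table has no built-in way to use such a time. The subject must be counted as event-free, counted as a failure, left out, or shown as unknown. The first three shift the estimate and the fourth gives no survival estimate.

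Phase II is single-arm with about 30 subjects, so its survival and duration results will be read against outside experience. If the method and the censoring rules are left open, the reported figure can depend on a choice made after the data are seen.

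**Working it through.** **1. The plan's own figures.** The documents contain no survival estimate, event count or assumed loss rate, so there is no survival figure to reproduce. The one design calculation does reproduce. Stopping at 2 or fewer responders in 14, and rejecting 20% with 8 or more in 24, gives an exact type I error of 0.0874 (limit 0.10) and power of 0.802 at a 40% CR rate (target 80%). The enrolment figure is 24/(1 - 0.20) = 30. This part concerns a binary endpoint and is sound.

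**2. Text check.** There are two ways to read Section 11.3.2.
- If the phrase covering all efficacy endpoints is taken literally, it includes response duration, PFS and OS, and the stated method does not handle censoring.
- If Section 7.1.2 limits efficacy to CR, CRi and CRp, the three time endpoints have no method at all.

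On both readings Section 11 lacks a time-to-event estimator, a censoring rule, and a time origin and event for each endpoint. Appendix A defines progression by marrow blasts but gives no definition of relapse after CR, which response duration needs.

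**3. How far a frequency summary could be off.** Assumptions, none of them in the documents: exponential survival with hazard λ = ln 2 / median; independent loss at constant hazard c per month; no other censoring before 36 months. The last follows Section 6.4, which counts 3 years from each subject's own on-study date. With h = λ + c, at 12 months:
- true OS = exp(-12λ)
- observed deaths D = (λ/h)(1 - exp(-12h))
- censored counted as alive: 1 - D
- censored counted as failures: exp(-12h)

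For a median of 6 months, λ = 0.1155 and true OS = 25.0%.
- c = 0.01: h = 0.1255, exp(-12h) = 0.222, D = 0.920 × 0.778 = 0.716. Counted as alive 28.4%; as failures 22.2%.
- c = 0.06: h = 0.1755, exp(-12h) = 0.122, D = 0.658 × 0.878 = 0.578. Counted as alive 42.2%; as failures 12.2%.

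The same formulas for other medians, with c from 0.01 to 0.06:

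| Assumed median OS | True 12-month OS | Censored counted as alive | Censored counted as failures |
|---|---|---|---|
| 3 months | 6.2% | 9.5-23.0% | 5.5-3.0% |
| 6 months | 25.0% | 28.4-42.2% | 22.2-12.2% |
| 12 months | 50.0% | 52.6-62.9% | 44.4-24.3% |

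With c = 0 every entry equals the true value, so the bias vanishes if nobody is censored before the landmark.

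**4. Whether Kaplan-Meier alone repairs OS.** Suppose survival status is not collected after progression. Assume monthly hazards of 0.25 for progression, 0.05 for death before progression and 0.25 for death after it.
- True 12-month OS = exp(-3.6) + 0.25 × exp(-3) × (1 - exp(-0.6))/0.05 = 0.027 + 0.112 = 0.140.
- Kaplan-Meier censored at progression sees only the 0.05 hazard and targets exp(-0.6) = 0.549.

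The estimate would be about 55% against a true value of about 14%. The cause is informative censoring, which the estimator cannot correct.

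**The case against.** The strongest reply is that Section 11.3.2 never names OS, PFS or response duration. Section 7.1.2 confines the efficacy outcomes to CR, CRi and CRp, and the second sentence of 11.3.2 speaks of response proportions. Section 11 also calls itself an overview. On that reading frequencies with confidence intervals are the right summary for binary response, and the time endpoints are simply not covered. This stands as far as it goes: the documents do not show that frequency tables were deliberately prescribed for survival. It does not remove the gap, because three stated objectives then have no method, and the same text has to be added.

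A reader might infer that the plan will produce wrong survival figures. The documents do not support that. With complete follow-up to a time point a simple proportion is unbiased, the plan promises no particular median or landmark rate, and a table could show censored subjects as a separate category.

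A reader might also infer that the recruitment period of about 48 months forces early censoring. It does not, since follow-up runs to 3 years from each subject's own on-study date. Only an analysis before follow-up is complete would add such censoring, and no section plans one.

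Finally, these are descriptive secondary objectives in a small trial, which limits the importance of the point.

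**Conclusion.** The concern holds as a gap in the analysis plan. The only stated efficacy method does not handle censoring, and no other method is given for response duration, PFS or OS, although the plan itself foresees loss and drop-out.

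The possible error is conditional. For a 6-month median OS and 1-6% monthly loss, a true 12-month OS of 25% would read about 3 to 17 points too high, or about 3 to 13 points too low, depending on how censored subjects are counted. The survival and loss rates are assumptions, and the bias is zero without early censoring.

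The follow-up rule may matter more for OS. Read literally, it ends contact at progression. The documents do not settle this, since Table 1 has a survival assessment under long-term follow-up that shares the same end points. The contrast of 14% and 55% shows what is possible under assumed hazards and is not a forecast.

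The primary CR analysis and the Simon design are not affected. The change should be made, but the trial's main conclusion does not depend on it.

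**What to change.** In Section 11.3.2, limit frequency tables with 95% confidence intervals to CR, CRi and CRp. For OS, PFS and response duration, state the time origin, the event (including what ends a response), the censoring rule and the analysis population. Report Kaplan-Meier estimates with medians, 6- and 12-month rates, 95% confidence intervals and median follow-up.

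Reconcile the follow-up rule in the synopsis, Table 1 footnote 13 and Section 6.4 with the OS objective, and state whether survival status is collected after progression. If it is not, a Kaplan-Meier curve censored at last contact should not be reported as OS.

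The cost is a few lines of analysis text. Continued survival-status contact is needed only if that status is not already captured after progression. Sample size and the primary decision rule stay as they are.

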12. EMERGENCY PROCEDURES

12.1 Emergency Contact

In emergency situations, the treating physician should contact the Principal Investigator by telephone at the number listed on the title page of the protocol.

12.2 Emergency Identification of Investigational Products

This is an open-label study; therefore, study drug will be identified on the package labeling.

12.3 Emergency Treatment

During and following a subject's participation in the study, the treating physician and/or institution should ensure that adequate medical care is provided to a subject for any adverse events, including clinically significant laboratory values, related to the study.

13. ADMINISTRATIVE CONSIDERATIONS

13.1 Good Clinical Practice

The procedures set out in this study protocol pertaining to the conduct, evaluation, and documentation of this study are designed to ensure that the Principal Investigator and Co-Investigators abide by Good Clinical Practice (GCP), as described in International Conference on Harmonization (ICH) Guideline E6 and in accordance with the general ethical principles outlined in the Declaration of Helsinki. The study will receive approval from an Institutional Review Board (IRB) prior to commencement. The Principal Investigator will conduct all aspects of this study in accordance with applicable national, state, and local laws of the pertinent regulatory authorities.

13.2 Delegation of Investigator Responsibilities

The Principal Investigator will ensure that all persons assisting with the study are adequately informed about the protocol, any amendments to the protocol, the study treatments, and their study-related duties and functions. The Principal Investigator will maintain a list of Co-Investigators and other appropriately qualified persons to whom he has delegated significant study-related duties.

13.3 Subject Information and Informed Consent

Before being enrolled in this clinical trial, the subject must consent to participate after the nature, scope, and possible consequences of the clinical study have been explained in a form understandable to him or her. An informed consent document that includes both information about the study and the consent form will be prepared and given to the subject. This document will contain all ICH, GCP, and locally required regulatory elements. The document must be in a language understandable to the subject and must specify the person who obtained informed consent.

After reading the informed consent document, the subject must give consent in writing. The written informed consent will be obtained prior to conducting any study-related procedures or tests. The subject's consent must be confirmed at the time of consent by the personally dated signature of the person conducting the informed consent discussions. A copy of the signed consent document must be given to the subject.

The PI will retain the original signed consent document. The PI will not undertake any measures specifically required only for the clinical study until valid consent has been obtained.

13.4 Confidentiality

Each subject will be assigned a unique acrostic that will contain no protected health information. The PI will retain a copy of the acrostic key in a locked office. Only the study number and unique acrostic will be recorded in the CRF, and if the patient's name appears on any other

document (e.g., pathologist report), it must be redacted before a copy of the document is placed in study files. Study files stored on a computer will be stored in accordance with local data protection laws. Subjects will be told that the IRB, UF Health Data Integrity and Safety Committee, or regulatory authorities may inspect their medical records to verify the information collected, and that all personal information made available for inspection will be handled in strictest confidence and in accordance with local data protection law.

13.5 Protocol Amendments

Once the study has started, amendments should be made only in exceptional cases. The changes then become part of the study protocol.

13.6 Record Retention

Essential documents will be retained by the PI for a minimum of 3 years after study closure at IRB. Essential documents include the following:

- Signed informed consent documents for all subjects;
- Subject identification code list, screening log, and enrollment log;
- Record of all communications between the PI and the IRB;
- Composition of the IRB;
- Record of all communications between the PI and the DISC;
- Composition of the DISC;
- List of Co-Investigators and other appropriately qualified persons to whom the PI has delegated significant study-related duties, together with their roles in the study, curriculum vitae, start/stop date(s) of participation, and their signatures;
- Copies of CRFs and of documentation of corrections for all subjects (for electronic case report forms [eCRFs], electronic files of the eCRF and audit trails will be utilized and provided to the site, as necessary);
- Drug accountability records;
- Record of any body fluids or bone marrow samples retained; and
- Other source documents (subject records, hospital records, laboratory records, etc.).

14. APPENDIX

This page intentionally left blank.

14.1 Appendix A: AML Response Criteria According to IWG

Response Criterion	Neutrophils (μL)	Platelets (μL)	Bone Marrow Blasts (%)	Other
CR	>1,000	>100,000	<5	Transfusion independent, no evidence of EMD
CRi (CR with incomplete blood counts)	<1,000	<100,000	<5	No evidence of EMD
CRp (CR with incomplete platelet recovery)	>1,000	<100,000	<5	No evidence of EMD
Disease Progression			> 25% increase from baseline	

Key: AML=acute myelogenous leukemia; CR=complete remission; EMD=extramedullary disease; IWG=International Working Group;

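### Appendix A's CR, CRi and CRp rows do not cover every remission: some subjects with marrow blasts below 5% and no extramedullary disease meet no row and, if that persists, go uncounted

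*Combined protocol and SAP*

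**What the plan says.** Appendix A (Section 14.1) has three remission rows, each with marrow blasts below 5%.

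- **CR:** neutrophils above 1,000, platelets above 100,000, and in the last column "Transfusion independent, no evidence of EMD".
- **CRi:** "CRi (CR with incomplete blood counts) <1,000 <100,000 <5 No evidence of EMD".
- **CRp:** "CRp (CR with incomplete platelet recovery) >1,000 <100,000 <5 No evidence of EMD".

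The only other row is disease progression. Partial remission and stable disease are used elsewhere in the protocol but have no row.

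Section 7.1.2 ties the outcome to this table: "The efficacy outcomes of interest will be CR (including CRi and CRp) as defined in" Appendix A. Section 11.1 also points there but names a shorter composite: "The primary intention is to determine the complete response rate (CR + CR_i, see" Appendix A). The synopsis lists all three categories. Section 11.1 tests a 20% null against 40%, stops if 2 or fewer of 14 evaluable subjects respond, and rejects the null at 8 or more of 24. Section 11.2.3 defines the efficacy population by one cycle of treatment and at least one efficacy assessment after dosing.

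**The concern.** A responder definition built from categories should place every possible subject, and better recovery should never lose a response. Appendix A fails on both counts. With blasts below 5%, no extramedullary disease and neutrophils below 1,000, a subject with platelets of 90,000 is CRi, while one with platelets of 110,000 meets no row.

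Low neutrophils without leukemia are foreseeable here. The fourth DLT criterion describes severe neutropenia lasting to Day 42 in the absence of leukemia. Section 4.2 plans for neutrophils below 500 at the Day 28 assessment, and Section 4.4.2 bars growth factors. How many of these subjects would have platelets above 100,000 is not stated.

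The decision counts are small, and the design has almost no spare power. One subject is 1/24 = 4.2 percentage points, and separates 2 from 3 of 14 or 7 from 8 of 24 when the count is at the boundary.

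**Working it through.** **1. Coverage of the table.** All combinations of neutrophils, platelets and transfusion status were set against the three rows, assuming blasts below 5% and no extramedullary disease.

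| Neutrophils | Platelets | Transfusion independent | Transfusion dependent |
|---|---|---|---|
| >1,000 | >100,000 | CR | none |
| >1,000 | <100,000 | CRp | CRp |
| <1,000 | <100,000 | CRi | CRi |
| <1,000 | >100,000 | none | none |
| exactly 1,000 | any | none | none |
| any | exactly 100,000 | none | none |

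Counting or omitting CRp in the endpoint changes none of the empty cells.

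**2. The plan's own design.** Inputs from Section 11.1: stage 1 of 14, stop at 2 or fewer; total 24, reject at 8 or more; null 0.20, alternative 0.40. With b(n, x, p) the binomial probability,

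P(reject | p) = sum over x = 3 to 14 of b(14, x, p) × P(Bin(10, p) ≥ max(0, 8 − x))

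P(stage 1 stop | p) = P(Bin(14, p) ≤ 2)

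At p = 0.20, P(reject) = 0.087. At p = 0.40 it is 0.802, with a stage 1 stop probability of 0.040. An exhaustive search returns the same minimax design, and 24/(1 − 0.20) = 30 enrolled. The stated design reproduces.

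**3. Illustration of loss.** Let f be the share of remissions that stay unclassified at the last assessment. The documents give no value for f, so it is assumed. The 40% is taken as the rate before loss, so the counted rate is 0.40 × (1 − f).

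| f (assumed) | Counted rate | Power | Stage 1 stop |
|---|---|---|---|
| 0 | 0.40 | 0.802 | 0.040 |
| 0.025 | 0.39 | 0.774 | 0.047 |
| 0.05 | 0.38 | 0.743 | 0.054 |
| 0.10 | 0.36 | 0.674 | 0.073 |
| 0.20 | 0.32 | 0.514 | 0.125 |

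The same loss applied to a true rate of 20% lowers the rejection probability from 0.087 to 0.068 (f = 0.05) or 0.052 (f = 0.10). The gaps therefore cost power and do not add false positives.

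**4. Effect of closing the gaps.** If the 20% null was set on the narrower definition, broadening the endpoint could raise the null rate. Mirroring the 5% and 10% above, 0.20 × 1.05 = 0.21 and 0.20 × 1.10 = 0.22 (assumed). P(reject) is then 0.110 or 0.135, against the stated limit of 0.10.

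**The case against.** **The consequence is not written down.** A reader might infer that the protocol scores these subjects as failures. No sentence says so. The row label, "CRi (CR with incomplete blood counts"), could lead an assessor to score CRi when either count is low, and the table prints no connector between the two thresholds. This stands as a limit on the wording: what can be said is that the stated thresholds leave the subject uncounted. It does not remove the problem. An either-count reading would make CRi overlap CRp, would still leave out the transfusion-dependent subject with recovered counts, and would not assign a count exactly at a threshold where neither count is low. In an open-label, single-arm trial, label and thresholds should not lead to different answers.

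**Cycle 2 can rescue a case.** Section 11.1 accepts a response at the end of any cycle, and Section 3.4 continues subjects without progression to Cycle 2, which ends with another marrow. This stands: only a pattern still present at the last assessment is lost.

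**The size is assumed.** This also stands. If the 40% in Section 11.1 already refers to the endpoint as tabulated, the stated power is not reduced at all. A reader might also infer that one or two such subjects would decide the trial; they would do so only at a boundary count.

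**Choice of blood count date.** A reader might infer that sites would pick the date that gives a category. The documents do not support that, because counts and marrow are tied to scheduled Day 28 visits.

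**Conclusion.** The table is incomplete and not ordered by recovery. It leaves unclassified a remission with isolated low neutrophils, one with recovered counts but continuing transfusion need, and one with a count exactly at a threshold. Because the primary endpoint rests on this table, such a subject, if unchanged at the last assessment, is in the denominator and not among the responders under the stated thresholds. That much follows from the text alone.

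The size does not. Losses of 5% or 10% would bring power to 0.743 or 0.674 and raise the stage 1 stop probability from 0.040 to 0.054 or 0.073. Both results rest on an assumed share and on reading 40% as the rate before loss. The sample size and stopping boundaries are not in error. The point should be corrected, since the edit is small and the endpoint decides the trial.

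**What to change.** Rewrite the three rows of Appendix A so that every subject with blasts below 5% and no extramedullary disease falls in exactly one:

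- **CR:** neutrophils at least 1,000, platelets at least 100,000, and transfusion independent.
- **CRp:** neutrophils at least 1,000 and platelets below 100,000.
- **CRi:** every other case, that is, neutrophils below 1,000 at any platelet count, or both counts recovered but still transfusion dependent.

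State the window over which transfusion independence is judged, since Appendix A gives none. Use the same composite, CR + CRi + CRp, in Sections 7.1.2 and 11.1, and report each category separately beside the total.

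The cost is wording. Blood counts and transfusions are already recorded at the study visits in Section 6.2, and the 14 and 24 subjects and their boundaries stay as they are. The downside is a slightly broader endpoint. Section 11.1 says "The CR rate for AML subjects receiving etoposide alone is approximately 20% (the null hypothesis"), without saying which categories that rate includes. The sponsor should confirm that it refers to the same composite; if it does not, the null rate and the attained type I error need to be rechecked before the rule of 8 in 24 is kept.
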